This study will include patients age 7 years or older with mutations in *RYR1* (confirmed by previous genetic testing), who are not currently taking antioxidants, and who are able and willing to perform all procedures at the time of enrollment. Children under age 7 may not be

able to successfully follow instructions for outcome measure testing. The accrual ceiling is 100. Withdrawals/dropouts will not be replaced. The target number of completers is 76.

Sixty to 100 age-matched healthy volunteers will be recruited.

NIH employees may participate. The NIH Information Sheet on Staff Research Participation will be provided to any staff member wishing to participate in this study (see Appendix L).

b. Inclusion criteria

Patients:

- Have a confirmed genetic diagnosis of RYR1-related myopathy, including congenital myopathy, OR have a clinical diagnosis of RYR1-related myopathy and a family member with a confirmed genetic diagnosis of RYR1-related myopathy
- Ambulatory.
- 7 years of age or older.
- Preferred: The affected subject has a previous muscle biopsy with available report confirming RYR1-related myopathy histopathology.

Healthy Volunteers:

- Ages 7 and older (15-25 7-12 year olds, 15-25 13-17 year olds, 15-25 18-40 year olds, 15-25 41 and older) without medical condition resulting in or complaints of muscle weakness and/or fatigue.
- The ability to provide consent.

c. Exclusion criteria

Patients:

- Adults who cannot provide their own consent and pediatric participants who do not have a parent able to provide consent
- Patients with a history of liver disease (Liver Function Tests will be collected at baseline and at each study visit as a precautionary measure). Liver disease is defined as moderate to severe hepatic impairment based on the following:
ALT \geq 8x upper limit of normal (ULN) with total bilirubin 2x ULN (plus >35% 'direct' bilirubin) and/or INR >1.5
or
GGT > 2-3x ULN with bilirubin 2x ULN (plus >35% 'direct' bilirubin) and/or INR >1.5
GGT >2-3x ULN and INR >1.5
- Patients with a history of peptic ulcers, gag reflex depression, and esophageal varices. Patients with gastrostomy tubes may be considered for participation, in the case of gag reflex depression or other swallowing or feeding difficulties.

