After data collection at six months, for each individual participant, the participant will immediately begin the second phase of the study when they will be randomized, using block randomization, to a placebo or a study drug group at the end of the 6-month visit to NIH. The allocation scheme is computer-generated using random permuted blocks to maintain balance of the two groups (placebo and control) and to maintain balance between children and adults. The participant will be randomized to the study drug or placebo group by an NIH pharmacist, who is blinded to the allocation scheme. Study drug assignments are recorded by the pharmacist, to be revealed only after the study is complete. BioAdvantex Pharma will provide oral effervescent NAC capsules, (PharmaNac) as well as identically packaged placebo capsules so that participants will not be able to distinguish the treatment from placebo. The study drug group will receive 15mg/kg/day (no more than 1800 mg/day) for the first week. After the first week, subjects who weigh fewer than 50kg will receive 30mg/kg/day of NAC (no more than 2700mg/day) divided TID over a period of six months. To increase compliance, as the tablets are formulated as 900mg each, subjects who weigh greater than 50kg will receive 2700mg/day.

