“Central Core Disease & Minicore: a place for support, learning & friends”, which is found at this link: <https://www.facebook.com/groups/243087794204/>. We will also tweet our study at <https://twitter.com/NINR> and use the web slide carousel on the NINR website

<https://www.ninr.nih.gov/researchandfunding/dir#.VzzUSRIrKRs>, to advertise our study.

A telephone or email prescreening will be used to determine preliminary eligibility (prescreen questionnaire, Appendix G). The prescreening telephone call will be scheduled or the prescreen questions will be sent via email. During the prescreening phase, we will request the potential participant send the results of their genetic testing confirming diagnosis of RYR1 (if done) and the results of their muscle biopsy confirming RYR1 histopathology (if done). We will receive these documents via mail, fax, or secure email before their visit. This will prevent patients who are clearly not eligible from making an unnecessary trip to NIH. The records of any participant who subsequently does not qualify will be destroyed or returned to the participant.

We will not request records of relatives of participants/potential participants who are enrolling under the criteria of a clinical diagnosis with a family member with confirmed RYR1.

There is no direct solicitation of employees/staff by supervisors. Direct solicitation by co-workers is considered improper.

c. Screening

Patients:

Informed consent will be obtained before any study procedures begin. We will screen participants by determining whether or not they meet inclusion/exclusion criteria by using the eligibility checklist (Appendix E).

At the onset of the study, individuals will be required to have a documented muscle biopsy confirming RYR1 diagnosis. If 20 individuals with this documentation cannot be recruited within the first 6 months, those without muscle biopsy confirmation will also be enrolled.

Healthy Volunteers:

Healthy volunteers will be screened by phone, email, or in-person for the presence of any neurological condition and/or complaints of weakness and fatigue and will be asked about current medications, per the eligibility criteria.

d. Study procedures

Patients:

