Motor Function Measure 32 (MFM): The MFM is a generic scale which provides a measurement of the effects of muscle weakness in neuromuscular diseases (NMD). Assessments are based on posture and movements of the whole body. It is applicable to both ambulant and non-ambulant patients with a wide range of disease severity. The patient is asked to roll, sit, lift head from prone and supine position, get up from a lying position, prop on arms, kneel, crawl, stand and step. This test will be combined with timed tests (floor to stand, ascend/descend 4 steps). Time to complete both tests: approximately 60 minutes.

6 Minute Walk (6MWT): The self-paced 6MWT assesses the submaximal level of functional capacity. The patient is asked to walk for 6 minutes with their best effort. A clinician accompanies the patient during the test to ensure patient's safety. Heart rate and blood pressure is monitored before and after exercise and after 5 minutes of recovery to ensure safety of the patient. The patient is allowed to stop if he feels tired. Time to complete the entire test: approximately 20 minutes.

Biodex: Biodex will be used to test muscle groups using a dynamic sub-max fatigue test with a repetitive motion. Blood pressure will be taken prior to testing to confirm the patient is not hypertensive (>140/90). Clinicians will assess participants for previous knee injury prior to testing. The biodex test will not be performed if the participant has a history of knee injury. Clinicians will provide a 5-minute break immediately after the test, during which time the patient may not rise from the seat. Time to complete the entire test: approximately 60 minutes.

Phlebotomy, Genetic Testing, and Exome Sequencing: Phlebotomy will be performed to obtain blood for liver function testing at baseline and glutathione levels. Blood and blood products may be analyzed or stored for creatine kinase (CK) level, lactate/pyruvate ratio, cell counts, blood chemistries, molecular genetic analysis and DNA banking. The lab will draw blood for DNA to confirm a genetic mutation, for exome sequencing, and/or for future studies and other clinical lab testing. If confirmatory genetic testing of an enrolled family member reveals that a participant does not have an *RYR1* mutation causative of RYR1-RM, the participant will be informed and withdrawn from the study.

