Date: July 2, 2018

RE: Statistical Analysis Plan for Protocol 15-NR-0072 Antioxidant therapy in RYR1-related congenital myopathy

Primary outcome measures

Where to find data (variables) for the below analyses in locked excel files:

- 1) AE_Spreadsheet_Demographics_LOCKED_2018.3.29
- 2) Urinelsoprostane_6MWT_LOCKED_2018.3.29
- 3) PillCount_PlasmaRedox_SalivaFBI_SMOxidativeStressDCFH_LOCKED_2018.3.29

Descriptive statistics

- Assess data distribution (i.e. basic descriptive statistics) for demographics (sex, ethnicity, smoking_status, alcohol_consumption, age_month0, height_month0, weight_month0, bmi_month0)

- Assess data distribution for urine isoprostane (all variables)

- Assess data distribution for six-minute walk test (predicted_distance_walked_month0, min_6_distance_month0, predicted_distance_walked_month6, min_6_distance_month6, predicted_distance_walked_month12, min_6_distance_month12).

- Assess data distribution for skeletal muscle oxidative stress (all variables),

- If possible, also assess data distribution for plasma redox (GSH_GSSG_month0, GSH_GSSG_month6, GSH_GSSG_month12, CYS_CYSS_month0, CYS_CYSS_month6, CYS_CYSS_month12).

- Assess data distribution for pill count (percent_compliance_month12).

- Descriptive statistics (frequency, mean, median, SD, SEM, IQR, range) for all the above for entire cohort at baseline (month 0) for demographics.
- Repeat abovementioned descriptive statistics split by treatment group (NAC and placebo) at baseline.
- Assess the frequency of AEs by system organ class (System Organ Class (SOC) (AE only) and by Preferred Term (Preferred Term (AE only)).

Natural history phase analyses

During the natural history phase of the study (month 0 to month 6), we will take one look at the data prior to the final analysis with the following two approaches:

1. After 30 participants complete their baseline visit, we will compare their baseline outcome measure values against healthy controls. The mean values for the primary outcome measures (corrected 15-F2t-isoprostane concentration and 6MWT distance) will be compared against existing data for otherwise healthy individuals using summary independent t-tests and/or standardized mean difference (i.e. Hedge's g which is a measure of effect size between two means, weighted by n). This analysis will be repeated when all baseline visits are completed.

Null Hypothesis (H_0)

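### Relatives may be enrolled with no one-per-family limit, but the natural-history, patient-versus-healthy and correlation analyses treat every patient as independent, so their standard errors can be too small

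*Protocol*

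**What the plan says.** **Who can enter.** Protocol Section 3.b (Inclusion criteria) requires either the patient's own genetic confirmation "OR have a clinical diagnosis of RYR1-related myopathy and a family member with a confirmed genetic diagnosis of RYR1-related myopathy". Section 4.b (Recruitment) refers again to people "enrolling under the criteria of a clinical diagnosis with a family member with confirmed RYR1" and says that records of those relatives will not be requested. Section 4.d (Phlebotomy, Genetic Testing, and Exome Sequencing) sets out a withdrawal rule that begins "If confirmatory genetic testing of an enrolled family member reveals that a participant does not have an" *RYR1* mutation that causes the disease. No section allows only one patient per family.

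**How patients are analysed.**
- Month 0 to 6 change: paired t-tests (Protocol Section 10.a; SAP, Natural history phase analyses, item 2; SAP, Secondary Outcome Measures).
- Patients against healthy people: the SAP compares the two primary measures with existing data "using summary independent t-tests" and/or Hedges' g. The secondary measures are handled in a similar way.
- Associations: Pearson and/or Spearman correlation (Protocol Section 10.a; SAP, secondary and exploratory sections).
- NAC against placebo: Student's t test in the protocol, and general linear models with individual-level covariates in the SAP.

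None of these has a family term or a clustered standard error, and the demographic variables listed in the SAP include no family identifier.

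**How patients are randomised.** Section 4.a allocates individuals by "random permuted blocks to maintain balance of the two groups (placebo and control) and to maintain balance between children and adults".

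**The concern.** Members of one family usually carry the same *RYR1* mutation. If their values resemble each other, two relatives bring less information than two unrelated patients. A t-test that counts them as two independent observations then reports a standard error that is too small.

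The patient-versus-healthy comparison matters most. The protocol gives its purpose as confirming that patients differ from healthy people so that the study can proceed with confidence. Standard errors that are too small there favour the expected result. For month 0 to 6 change the protocol expects no difference, so the same fault would produce spurious findings of change and would work against the investigators' expectation.

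**Working it through.** **1. The plan's own figure.** Section 10.b assumes changes of 1.7 (SD 2.34) and 0 (SD 2.80), two-sided alpha 0.05 and 80% power.

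Normal approximation: n = (1.960 + 0.842)² × (2.34² + 2.80²) / 1.7² = 7.849 × 13.316 / 2.89 = 36.2, so 37 per group. With the Satterthwaite t-test, 37 per group gives 79.8% power and 38 gives 80.9%. The stated 38 per group (76 completers) reproduces. Like the tests, it assumes independent patients.

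**2. Inputs not in the documents (assumed).** The share f of patients with an enrolled relative is 10-60%, in families of m = 2. The within-family correlation ICC of the analysed quantity is 0.1-0.5.

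**3. Formulas.** Design effect DE = 1 + f(m − 1) × ICC. The true standard error is √DE times the reported one. The reported interval is too narrow by 1 − 1/√DE. The true two-sided error is 2 × [1 − Φ(1.96/√DE)]. The effective sample size is N/DE.

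| f | ICC | DE | Interval too narrow by | True error | Effective N of 30 | Effective N of 76 |
|---|---|---|---|---|---|---|
| 10% | 0.1 | 1.01 | 0.5% | 5.1% | 29.7 | 75.2 |
| 20% | 0.3 | 1.06 | 2.9% | 5.7% | 28.3 | 71.7 |
| 20% | 0.5 | 1.10 | 4.7% | 6.2% | 27.3 | 69.1 |
| 40% | 0.5 | 1.20 | 8.7% | 7.4% | 25.0 | 63.3 |
| 60% | 0.5 | 1.30 | 12.3% | 8.6% | 23.1 | 58.5 |

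Simulating the one-sample or paired t-test with related pairs (40,000 runs) agrees: about 6.2% at f 20% and 7.4% at f 40%, both with ICC 0.5. With f = 0 or ICC = 0, DE = 1 and nothing changes.

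**4. Patients against healthy people.** Only the patient side is clustered. With equal variances, the variance ratio is (DE/n + 1/h) / (1/n + 1/h), where n is the number of patients and h the number of healthy people. Take DE = 1.20 and n = 76:
- h = 80, within the planned 60-100 volunteers: (0.01579 + 0.01250) / (0.01316 + 0.01250) = 1.10, true error about 6.2%. At the first look, with n = 30, the ratio is 1.15 and the error about 6.7%. Simulation gives 6.0-6.5% and 6.7-6.8% respectively.
- h = 1881, the size of the isoprostane reference set cited in Section 10.b: (0.01579 + 0.00053) / (0.01316 + 0.00053) = 1.19, true error about 7.3%, close to the full design effect.

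**5. Correlations.** When there is no association, the variance of r grows by about 1 + f(m − 1) × ICC₁ × ICC₂, where the two ICCs belong to the two variables. At f = 60% and both ICCs 0.5 this is 1 + 0.6 × 0.25 = 1.15, a true error of about 6.8%. The inflation is therefore smaller than for means.

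**6. NAC against placebo.** With related pairs in the sample and allocation made without regard to family, the simulated error of the t-test was 4.6-5.3%. It is not inflated.

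**The case against.** **Co-enrolment is permitted but not shown.** The confirmed relative in the inclusion criterion may be outside the trial. In the Section 4.d rule, the enrolled family member and the participant without the mutation may be the same person. Section 3.a describes patients as genetically confirmed, and Section 11.a gives them priority. This stands: the point is conditional on relatives having enrolled.

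**A shared mutation does not fix the ICC.** Section 10.a notes that patients with identical mutations occasionally differ in phenotype. The introduction describes the disease as non-degenerative and often stable for years, so 6-month changes may be almost uncorrelated within families even where levels are similar. This also stands, and it makes the patient-versus-healthy comparison the more exposed of the two.

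**The success criterion is untouched.** Success is defined on the NAC-versus-placebo isoprostane difference, which keeps its type I error. This stands in full.

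**A stronger reading.** A reader might infer that relatives in one home, allocated to opposite arms, would mix products or break the blind. The documents do not support this. They say nothing about shared homes or shared product, the placebo is identically packaged, and enrolment is rolling, so relatives need not be on treatment together. A reader might also infer that the treatment models need a family term. Individual randomisation protects their error rate, so that does not follow.

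**Conclusion.** The point holds as a conditional weakness of the natural-history, patient-versus-healthy and correlation analyses. It needs two facts that the documents do not give: that relatives enrolled, and that the analysed values are positively correlated within families. Over the assumed range the effect runs from negligible (true error 5.1%) to moderate (8.6%, with intervals 12% too narrow). The upper end applies to one-sample or paired tests, and nearly to comparisons with a large external reference set. Against 60-100 volunteers it is smaller, and for 6-month changes it may vanish. Larger families would raise it: families of three at f 40% and ICC 0.5 give DE = 1 + 0.4 × 2 × 0.5 = 1.40 and a true error of 9.8%. The randomised comparison is not affected in this way. Only the sponsor can say how many relatives took part, and the remedy is cheap enough to apply whatever the answer.

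**What to change.** Add a family identifier to the analysis data, and report the number of families and of related patients. If no patients are related, one sentence saying so closes the point. Otherwise, use family-clustered (cluster-robust) standard errors or a family random intercept in the Phase 1, patient-versus-healthy and correlation analyses.

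The summary t-tests and Hedges' g work from means and SDs. The standard error on the patient side should therefore come from the clustered patient-level analysis.

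Optionally, run the primary treatment models once more with one member per family as a sensitivity analysis. It discards randomised patients and depends on which member is drawn, so it should not replace the main analysis. The primary treatment models need no family term.

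**Cost.** The SAP names files already locked, so the identifier has to be added as a documented supplement, for example from the family history taken at enrolment. No new patients, visits or changes to allocation are needed. Intervals in the Phase 1 analyses become slightly wider. If most families have a single member, a random intercept may be poorly estimated, and cluster-robust standard errors are then the simpler choice.
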